8.6.4 Additional Secondary Analyses

Analysis of additional secondary efficacy endpoint 1: The percentage of responders at maximum frown (as defined above for the primary efficacy endpoint) at week 12 (after the first treatment with BoNT/A-DP or placebo).

The same analyses, inclusive of the additional exploratory analyses, as described for the primary endpoint will be conducted. However, a sensitivity analysis using a tipping point analysis will not be performed.

Analysis of additional secondary efficacy endpoint 2: The percentage of responders at maximum frown (as defined above for the primary efficacy endpoint) at week 16 (after the first treatment).

The analysis of the week 16 visit will be conducted on observed values only, i.e., missing investigator or the subject in-clinic assessments with the FWS at baseline or week 16 visit will be excluded from analysis but not assigned as being non-responders. Subjects who were re-treated before visit week 16 are considered to be non-responders.

In addition, the same analyses, inclusive of the additional exploratory analyses, as described for the primary efficacy endpoint will be conducted as exploratory analyses. However, a sensitivity analysis using a tipping point analysis will not be performed. Subjects who were re-treated before visit week 16 are considered to be non-responders in all these analyses.

Analysis of additional secondary efficacy endpoint 3: The percentage of responders at maximum frown (as defined above for the primary efficacy endpoint) at week 20 or later (after the first treatment).

The analysis of percentage of responders at week 20 (after the first treatment) will be conducted on observed values only, i.e., missing investigator or the subject in-clinic

Statistical Analysis Plan (SAP)

CROMA
est. 1976

assessments on FWS at baseline or visit week 20 will be excluded from the analysis but not assigned as being non-responders. Subjects who were re-treated before visit week 20 are considered to be non-responders.

In addition, the same analyses, inclusive of the additional exploratory analyses as described for the primary efficacy endpoint, will be conducted as exploratory analyses (for select subgroups also). However, a sensitivity analysis using a tipping point analysis will not be performed.

Analysis of additional secondary efficacy endpoint 4: The proportion of subjects with a ≥ 1 point reduction in FWS score at rest at week 4 in the first treatment cycle, based separately on the investigator and the subject in-clinic assessments

In general, the same statistical analyses, inclusive of the additional exploratory analyses as described for the primary efficacy endpoint, will be conducted. However, a sensitivity analysis using a tipping point analysis will not be performed.

All analyses (inclusive the additional exploratory analyses) on the investigators' in-clinic assessment will be conducted only for subjects who have an investigators' in-clinic assessment of a FWS score at rest ≥ 1 at baseline. This will similarly be applied for the analyses of the subjects' in-clinic assessment.

For the primary analysis, subjects with missing investigator in-clinic assessments of FWS score at rest at baseline or week 4 visit will be assigned as being non-responders for this efficacy endpoint. This will similarly be applied for the subjects' in-clinic assessment within the primary analysis.

As a consequence, the primary analysis of this endpoint will lead to exactly the same results as the LOCF analysis (as a subject with missing week 4 is considered as a non-responder) and thus the LOCF analysis will be skipped.

Analyses of other visits after first treatment but before re-treatment up to week 48 are exploratory only based on the FAS population using descriptive statistics only. Subjects with re-treatment before the respective visit will be excluded from the analysis. Additional exploratory analyses, as described for the primary efficacy endpoint, will not be conducted, with the exception of the calculation of 95% CIs.

Other additional secondary endpoint analyses:

Other additional secondary efficacy endpoints will be analyzed applying the appropriate statistical method for the comparison of both treatment arms. For proportions

Statistical Analysis Plan (SAP)

CROMA
est. 1976

- of responders with a FWS score of 0 or 1 and an improvement ≥ 2 points in FWS score at maximum frown (composite endpoint, at weeks 1, 2 and 8),
- of subjects with ≥ 2 and ≥ 1 point reduction in FWS at maximum frown (at baseline and visits 2, 4, 12, 16 and 20 weeks after treatment, within the first treatment cycle),
- of subjects with a ≥ 1 point reduction in FWS at rest, relative to baseline
- of subjects with an improvement of ≥ 2 points in FWS at maximum frown at 4 weeks after re-treatment,
- of subjects with ≥ 1 point reduction in FWS score at maximum frown (at weeks 1, 2, 4, 8, 12, 16 and 20 relative to baseline,
- of subjects with ≥ 1 point reduction in FWS score at maximum frown at week 4 relative to re-treatment baseline,

the CMH test (with stratification variable site) and the Pearson χ^2 -test will be applied. In case of a total number of observations below 30, or in case of at least one cell frequency below 5, Fisher's exact test will be used instead of the χ^2 -test. Two-sided 95% CIs for response rates will be calculated, where appropriate. Additionally, the cumulative proportions of effects at weeks 1, 2, and 4 will be calculated.

Time to onset of effect in the first treatment cycle will be analyzed descriptively and by using the Kaplan-Meier method. Moreover, the daily assessments of the line severity when frowning will be analyzed descriptively. The FACE-Q satisfaction with outcome scale will be analyzed descriptively.

All efficacy endpoints, with the exception of “responder” 4 weeks after re-treatment, will be analyzed for the first treatment cycle only. The analysis of “responder” 4 weeks after re-treatment will be conducted on observed values only, i.e., subjects with missing investigator or the subject in-clinic assessments on FWS week 4 or at the preceding end of the cycle visit will be excluded from analysis. Subjects who were treated with placebo during the first treatment cycle are excluded from the analysis of this endpoint, but not assigned as being non-responders. A two-sided McNemar test (using a significance level of 0.05) will be used to compare the response proportions between week 4 re-treatment visit and at the preceding end of the cycle visit. These endpoints will be separately analyzed for each open label extension cycle.

In addition to the FAS population, the analyses of these endpoints will also be based on the MFAS and PP populations. For all analyses, a one-sided significance level of 0.025 will be used, if not stated otherwise. Additional exploratory subgroup analyses will be conducted as described in Section 8.8.

Statistical Analysis Plan (SAP)

CROMA
est. 1976

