6.3.2 Open Label Extension

After the first treatment cycle is completed, all subjects may enter the open label extension phase and will be dosed with BoNT/A-DP (20 U) for subsequent re-treatments.

Subjects will attend for visits at 1 and 4 weeks after re-treatment and at 4-weekly intervals thereafter. Additional telephone call follow-ups will take place in the open label extension phase two and eight weeks after each re-treatment. Each re-treatment cycle will last at least 12 weeks and will end when the subject qualifies for re-treatment (in accordance with the "eligibility for re-treatment criteria" as outlined in Section 7.3) or with the End of Study visit (see below). According to the study schedule (Section 2.2), a maximum of 4 treatments per subject (4 treatment cycles) is permitted during the study time frame, with treatments separated by a minimum of 12 weeks.

A subject may move to the next treatment cycle if more than 12 weeks have passed since the previous treatment. Starting at week 12 and at 4-weekly intervals thereafter, subjects will attend the site for the Evaluation for Re-treatment visit. If the subject has a FWS score (at maximum frown) of ≥ 2, as determined by both the subject and the investigator, this visit on the same day at the same site visit will then be considered the End of Cycle visit and all other criteria required to determine eligibility for re-injection will be assessed e.g. negative urine pregnancy test (in women of child-bearing potential), lack of infection or inflammation in the planned injection area etc. Furthermore, all additional tests e.g. laboratory tests required for final cycle assessment will be performed (as outlined in the Schedule of events, Section 2.1). If the subject qualifies for re-treatment, on the same day at the same site visit, the subject will then enter the next treatment cycle and will receive the next study drug treatment as part of the Re-Treatment visit (i.e. day 0 of the next treatment cycle).

If the FWS score (at maximum frown) is assessed as ≥2 by both the investigator and the subject, but the additional criteria for reinjection are not met, e.g. relevant infection or inflammation at the injection site, the subject may attend for a visit 4 weeks thereafter. Subjects with a positive pregnancy test, or subjects who do not agree to re-treatment, will be withdrawn from the study and the End of Study visit will be conducted at the earliest opportunity.

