The analysis of the week 16 visit will be conducted on observed values only, i.e. missing investigator or the subject in-clinic assessments with the FWS at baseline or week 16 visit will be excluded from analysis but not assigned as being non-responders. Subjects who were retreated before visit week 16 are considered to be non-responders.

In addition, the same analyses, inclusive of the additional exploratory analyses, as described for the primary endpoint will be conducted.

Analysis of additional secondary endpoint 3: The percentage of responders at week 20 or later (after the first treatment).

The analysis of percentage of responders at week 20 (after the first treatment) will be conducted on observed values only, i.e. missing investigator or the subject in-clinic assessments on FWS at baseline or visit week 20 will be excluded from the analysis but not assigned as being non-responders. Subjects who were re-treated before visit week 20 are considered to be non-responders.

In addition, the same analyses, inclusive the additional exploratory analyses as described for the primary endpoint, will be conducted (for subgroups also).

Analysis of additional secondary endpoint 4: The proportion of subjects with $a \ge 1$ point reduction in FWS score at rest at week 4 in the first treatment cycle, based separately on the investigator and the subject in-clinic assessments

In general, the same statistical analyses, inclusive of the additional exploratory analyses as described for the primary endpoint, will be conducted.

The analysis on the investigator's in-clinic assessment will be conducted only for subjects who have an investigator's in-clinic assessment of a FWS score at rest ≥ 1 at baseline. This will similarly be applied for the analysis of the subject's in-clinic assessment.

Subjects with missing investigator in-clinic assessments at baseline or week 4 visit will be assigned as being non-responders for this endpoint. This will similarly be applied for the subject's in-clinic assessment.

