If at an Evaluation for Re-treatment visit the subject wants to get re-treated, but the investigator does not agree or vice versa (i.e., the FWS score is not \geq at least 2 by both assessments), the subject will return to the site four weeks thereafter for another Evaluation for Re-treatment visit. There is no limit to the number of Evaluation for Re-treatment visits. In order to consider a visit as the End of Cycle visit, there must always be agreement between investigator and subject on a FWS score (at maximum frown) of ≥ 2 .

End of Study Visit

The End of Study visit can take place in four-weekly intervals from study-week 48 until study-week 60. The last study drug re-treatment will be administered no later than week 48. For subjects receiving a re-treatment at week 48, the last cycle will end 12 weeks later at week 60 (i.e., End of Study visit).

The End of Study visit will take place at week 48 if the week 48 visit is an Evaluation for Re-treatment visit and the subject does not meet the criteria for re-treatment in case this visit is 12 or more weeks after the last treatment. As week 48 is the last possible time point for re-treatment, such subjects will continue with all additional assessments of the End of Study visit on the same day. For subjects having received their last injection eight weeks or less prior to week 48, the End of Study visit will take place 12 weeks after the last study drug treatment was given, e.g. week 52 if the subject was re-treated at week 40.

For subjects who are prematurely discontinued from the study (at any time), the End of Study visit will take place within one week of discontinuation.

A detailed description of procedures and assessments to be conducted during this study is summarized in the Scheduled of Study Assessments in Table 1 below.

COVID-19 Pandemic

Due to the COVID-19 pandemic, which touched the world mainly the first 6 months of 2020, it has been allowed that visits were done remotely instead of physically when site was closed.

All re-treatments were put on hold between the 16th March and 5th May 2020 due to concerns that the subject will not be able to return for Week 1 and Week 4 assessments. Consequently, when a subject was eligible for re-treatment at a visit, the injection has been delayed until the subject could go back to site (if the injection is done before or at Week 48).

	Statistical Analysis Plan (SAP)	croma est. 1976
---	--	---------------------------

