7.2 Handling of Missing Data

7.2.1 Missing Data Analysis Methods

Analyses will be performed by visit. For responder analyses on visits at week 4 and week 12, missing in-clinic assessments (investigator or the subject) with the FWS at baseline or week 4 and week 12 visits will be assigned as being non-responders.

As sensitivity analyses, the following additional approaches for handling of missing values will be applied:

Statistical Analysis Plan (SAP)

CROMA
est. 1976

- Analysis on observed values only, i.e., missing values will be excluded from analysis.
- Last observation carried forward (LOCF).
- Tipping point analysis: each missing value will be assigned to either a response or non-response, so that all possible combinations of replacing one or more missing values within each treatment group will be analyzed. P-values will be calculated for each combination and graphically displayed using a scatter plot.

The analysis of the week 16 visit regarding the efficacy endpoint “percentage of responders at week 16 (after first treatment)” will be conducted on observed values only, i.e., missing investigator or the subject in-clinic assessments with the FWS at baseline or week 16 visit will be excluded from analysis but not assigned as being non-responders. Subjects who were re-treated before visit week 16 are considered to be non-responders. The same approach holds for the efficacy endpoint “percentage of responders at week 20 or later (after first treatment)” respectively. The analysis of the additional secondary efficacy endpoints “proportion of subjects with ≥ 1 point reduction in FWS score (at maximum frown) in the BoNT/A-DP and placebo groups during the first treatment cycle at week 16 and week 20 relative to baseline, based on both the investigators’ and the subjects’ in-clinic assessments” will be conducted in a similar manner on observed values only.

All analyses of the modified Skindex-16 (GL-QoL) Emotional and Social Functioning domains and overall scores will be conducted on observed values only, i.e., missing domain and overall scores will be excluded from analysis; no imputation of missing domain and overall scores will be performed. The same approach will be followed for the analyses of the FACE-Q scales.

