11 APPENDICES

Appendix A - Visit Window

Analyses will be performed by nominal visit, irrespective of any time window deviations. For the End of Study (EOS) visit, the following criteria will be applied only for the efficacy dataset ADQS:

- The nominal visit (i.e. END OF STUDY) will be used throughout for all subjects who have not discontinued.
- For discontinued subjects, the EOS data will be mapped to the latest scheduled visit prior to EOS study day (based on ADY). If assessments are available at this visit, then data will be mapped to the visit following this preceding visit.
- Unless duplicate records are present in the database, there should be no duplicate data per visit.

The following examples illustrate the approach:

Criteria (ii):

[figure not shown]
	Subjid	VISIT	VISITNUM	ADT	ADY
1	xxxx	SCREENING	1	20MAY2019	-11
2	xxxx	BASELINE DAY 0	2	30MAY2019	1
3	xxxx	CYCLE 1 WEEK 1	3	10JUN2019	11
4	xxxx	CYCLE 1 WEEK 2	4	14JUN2019	15
5	xxxx	END OF STUDY	28	19JUL2016	50

For this subject, End of Study visit will be assigned to CYCLE 1 WEEK 4 visit.

Criteria (iii):

	Subjid	VISIT	VISITNUM	ADT	ADY
1	xxxx	SCREENING	1	28JUL2019	-12
2	xxxx	BASELINE DAY 0	2	09AUG2019	1
3	xxxx	CYCLE 1 WEEK 1	3	18AUG2019	10
4	xxxx	CYCLE 1 WEEK 2	4	25AUG2019	17
5	xxxx	CYCLE 1 WEEK 4	5	07SEP2019	30
6	xxxx	CYCLE 1 WEEK 8	6	08OCT2019	59
7	xxxx	CYCLE 1 WEEK 12	7	01NOV2019	85
8	xxxx	END OF STUDY	28	12JAN2020	158

For this subject, End of Study visit will be assigned to CYCLE 1 WEEK 20 visit (i.e., End of study visit study day is compared versus the last possible visit study day [Study day of Cycle 1 Week 20 = 141] before End of study).

Statistical Analysis Plan (SAP)

CROMA
est. 1976

Criteria (iii):

	Subjid	VISIT	VISITNUM	ADT	ADY
1	xxxx	SCREENING	1	03AUG2019	-6
2	xxxx	BASELINE DAY 0	2	09AUG2019	1
3	xxxx	CYCLE 1 WEEK 1	3	16AUG2019	8
4	xxxx	CYCLE 1 WEEK 2	4	23AUG2019	15
5	xxxx	CYCLE 1 WEEK 4	5	06SEP2019	29
6	xxxx	CYCLE 1 WEEK 8	6	14OCT2019	67
7	xxxx	CYCLE 1 WEEK 12	7	01NOV2019	85
8	xxxx	END OF STUDY	28	14DEC2019	128

For this subject, End of Study visit will be assigned to CYCLE 1 WEEK 16 visit (i.e., End of study visit study day is compared versus the last possible visit study day [Study day of Cycle 1 Week 16 = 113] before End of study).

Note: The PP population will be based on the CRF visits i.e. if EOS visit is allocated to CYCLE 1 WEEK 4, the subject will still be excluded from PP population for having CYCLE 1 WEEK 4 missing.

Numbering of Visits

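### At weeks 16 and 20, a relapsed subject with no re-treatment and no later rating leaves the denominator, while an identical re-treated subject counts as a failure

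*SAP*

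**What the plan says.** SAP 7.2.1 and 8.6.4 define the main analysis of the week-16 responder rate on observed values. Subjects whose investigator or subject rating is missing at baseline or at the visit "will be excluded from analysis but not assigned as being non-responders". The one exception is that "Subjects who were re-treated before visit week 16 are considered to be non-responders". Week 20 is handled the same way; Protocol 12.4.2 has "Subjects who were re-treated before visit week 20 are considered to be non-responders". At week 12 the rule is the reverse: a missing rating is a non-response (SAP 7.2.1).

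Protocol 6.3.2 sets out what follows relapse, meaning FWS 2 or more at maximum frown by both raters at an evaluation visit from week 12 on:

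- Subjects who qualify and accept are re-treated.
- "Subjects with a positive pregnancy test, or subjects who do not agree to re-treatment, will be withdrawn from the study", with an End of Study visit as soon as possible.
- If another criterion fails, such as infection at the injection site, "the subject may attend for a visit 4 weeks thereafter".

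SAP Appendix A places a discontinued subject's End of Study data at the last scheduled visit before that day or, if that visit already has data, at the following one. Under Protocol Table 9-1 (footnotes 10 and 11), when termination is decided at a site visit the End of Study procedures belong to that visit, and assessments already done that day need not be repeated.

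**The concern.** Non-response is tied to re-treatment, not to the relapse that leads to it. Take two subjects, both rated 2 or more by both raters at week 12. Neither is a responder, since response requires 0 or 1. One accepts re-treatment and is a failure at weeks 16 and 20. The other declines and is withdrawn, and if no later rating exists the subject is removed from the analysis. Everyone removed this way was last seen as a non-responder, so removal can only push the rate up.

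Duration of effect against placebo is a stated secondary objective (Protocol 5.3, SAP 2.2). Kaplan-Meier analysis is planned for onset only, so the late responder rates carry most of the evidence on duration. The switch in missing-data rule between week 12 and week 16 also means that the time course is not read on one basis.

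**Working it through.** **Which relapsed, un-re-treated subjects are dropped.** Reading Protocol 6.3.2 and 6.3.3, Table 9-1 and SAP Appendix A together:

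| Relapse at | Later rating | Week 16 | Week 20 |
|---|---|---|---|
| Week 12 | Returns at weeks 16 and 20, still FWS 2 or more | Non-responder | Non-responder |
| Week 12 | Separate End of Study visit within a week | Non-responder (mapped to week 16) | **Dropped** |
| Week 12 | End of Study same day, FWS not repeated | **Dropped** (Appendix A does not settle this) | **Dropped** |
| Week 12 | No End of Study visit | **Dropped** | **Dropped** |
| Week 16 | Separate End of Study visit within a week | Non-responder | Non-responder (mapped to week 20) |
| Week 16 | Same day without repeat, or no End of Study visit | Non-responder | **Dropped** |

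**Size.** The documents give no figure for the effect of this rule, so there is none to reproduce. Let p be the active rate with these relapsers counted as failures, and m the share of the arm that is dropped. Then

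reported rate = p / (1 − m).

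m is not in the documents. Two illustrative assumptions:

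- m = 1%, about 3 of the roughly 265 active subjects (353 × 3/4 = 264.75).
- m = 5.8%, about 15 of 265. This borrows all active-arm non-completion of the double-blind phase in BLESS I (Protocol 4.4.2.1): 500/531 = 94.2% completed, as stated, so 31/531 = 5.8% did not.

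For p of 10% and 20%:

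- m = 1%: 10/0.99 = 10.1% (+0.1 points); 20/0.99 = 20.2% (+0.2).
- m = 5.8%: 10/0.942 = 10.6% (+0.6); 20/0.942 = 21.2% (+1.2).

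This range of p is suggested by the earlier studies' composite rates for at least 1 point of improvement (Protocol 4.4.2.1 and 4.4.2.2), which is a looser definition than response here:

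| Proxy rate | m = 1% | m = 5.8% |
|---|---|---|
| BLESS I week 16, 20.8% | 21.0% | 22.1% |
| BLESS II week 16, 12.1% | 12.2% | 12.8% |
| BLESS I week 20, 9.9% | 10.0% | 10.5% |
| BLESS II week 20, 4.7% | 4.7% | 5.0% |

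Placebo rates on the same proxy were 0 to 0.6%, so dividing them by (1 − m) hardly moves them. The treatment difference shifts by nearly the same amount as the active rate.

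**The case against.** The best defence is that the plan already limits the damage, and most of that defence stands.

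- A reader might infer that relapse counts as failure only if the subject is re-treated. That is not so: anyone rated 2 or more at week 16 or 20 is an observed non-responder.
- A reader might infer that everyone who cannot be re-treated is withdrawn. Only refusal and pregnancy lead to withdrawal in Protocol 6.3.2; a subject deferred for infection may return and be rated.
- Appendix A does rescue the week-12 relapser with a separate End of Study visit, at week 16 but not at week 20.
- SAP 8.6.4 also applies the primary-endpoint analyses at weeks 16 and 20 as exploratory analyses. These include missing = non-responder and LOCF, and both would count these subjects as failures. However, they supplement an observed-values main analysis. The week-16 list in SAP 8.9 names observed values only, omits the LOCF that it lists for week 12, and says that those analyses will not be repeated at the final analysis. The two sections do not agree on what will be run.
- It is tempting to add subjects caught by the pandemic, when "All re-treatments were put on hold between the 16th March and 5th May 2020". The hold delayed injections and did not withdraw anyone, and the documents do not say whether any affected subject was still in cycle 1. That limb is conditional only.
- The 5.8% neither estimates nor bounds m. BLESS I non-completers may include subjects lost before week 12 with no recorded relapse, and a subject who relapses and then declines may be recorded as having completed cycle 1 (Protocol 9.5 documents that separately).
- Sampling error is larger than the shift: with 265 subjects the 95% half-width is 1.96 × √(0.1 × 0.9/265) = 3.6 points at 10%, and 4.8 points at 20%. This limits the importance of the bias but does not remove it.

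**Conclusion.** The gap is real but narrow. It follows from a stated rule: every missing rating is excluded unless the subject was re-treated. It bites at week 20 after a week-12 relapse, and at either visit when the End of Study visit is absent or falls on the relapse day without a repeat FWS. Its direction is known, provided that relapsed subjects do not regain response untreated. Its size is not known. On the illustrative shares it is about 0.1 to 1.2 points on a 10–20% rate, and these figures should not be read as an estimate.

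A reader might infer that a claim of efficacy is at risk. The documents do not support that: SAP 8.6.1.1 makes all additional secondary endpoints exploratory, the hierarchical tests do not use these data, and placebo rates are near zero. What is affected is the description of duration, which will look slightly better than it should.

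**What to change.** Add to SAP 7.2.1 and 8.6.4, for the week-16 and week-20 responder endpoints:

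> A subject who met the End of Cycle FWS criterion (2 or more at maximum frown by both investigator and subject) at or after week 12 and has no in-clinic cycle-1 FWS at the visit analysed is a non-responder at that visit, whether or not re-treated.

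Keep later observed ratings as observed. A rule that made every earlier relapse a permanent failure would override real data (for example, in a subject deferred for infection) and turn the endpoint into sustained response. Keep exclusion for subjects lost without a recorded relapse. Do not carry the sentence over to the endpoints for a reduction of at least 1 point: a subject who goes from 3 to 2 meets this relapse criterion and still has a 1-point reduction.

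Also reconcile SAP 8.6.4 with SAP 8.9 on which supplementary analyses are run at week 16.

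The cost is one sentence and a small programming change. The ratings needed are already collected at every evaluation visit. The late responder rates will come out slightly less favourable.

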3.3 Study Treatments and Assessments

Subjects will participate in this study for a duration of 50 to 62 weeks from signing the informed consent form (ICF) to the End of Study visit (i.e., up to 14 calendar days for screening, followed by 48 to 60 weeks study participation).

Subjects will receive a maximum of four permitted rounds of treatment, with a minimum interval between treatments of 12 weeks.

The first treatment cycle of the study will comprise of two treatment groups as follows:

- Group A (active): BoNT/A-DP (20 units, 0.5 mL).
- Group B (placebo control): sterile, 0.9% sodium chloride (0.5 mL).

An interim analysis (IA) will be performed when all subjects complete the re-evaluation for retreatment visit at week 16 of the first treatment cycle or complete the double blind phase (whichever occurs earlier). Refer to Section 8.9 for more details regarding the IA.

Eligible subjects will be randomized at baseline (day 0) to Group A or B to receive the first treatment in a 3:1 randomization scheme, respectively. Investigators and subjects will be blinded to the treatment administered and will evaluate the severity of glabellar lines independently. The subjects must perform their assessment independently and ideally before the investigator, to ensure they are not biased by the investigator. The same investigator must assess the subject at baseline and at the visits at weeks 1, 2 and 4 in the first treatment cycle.

After a screening period of up to 14 calendar days, subjects will receive the first treatment (BoNT/A-DP or placebo) and attend for visits at 1, 2 and 4 weeks after treatment and at 4-

Statistical Analysis Plan (SAP)

CROMA
est. 1976

weekly intervals thereafter for evaluation of efficacy and safety (primary and key secondary efficacy endpoints will only be evaluated in the first treatment cycle in comparison with placebo). Re-screening will not be permitted.

The effect of botulinum toxin typically lasts a few months, hence the first treatment cycle will last at least 12 weeks and will end when the subjects qualify for re-treatment.

Open Label Extension

After the first treatment cycle is completed, all subjects may enter the open label extension phase and will be dosed with BoNT/A-DP (20 U) for subsequent re-treatments.

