11. The percentage of subjects with a FWS score of 0 or 1 and an improvement of ≥ 2 points in FWS score at maximum frown (investigator and subject assessment) at four weeks after re-treatment relative to the rating at the preceding end of cycle visit.
12. The proportion of subjects with ≥ 1 point reduction in FWS score (at maximum frown) in the BoNT/A-DP and placebo groups during the first treatment cycle at weeks 1, 2, 4, 8, 12, 16 and 20 relative to baseline, based on both the investigators' and the subjects' in-clinic assessments.
13. The proportion of subjects with ≥ 1 point reduction in FWS score (at maximum frown) in the BoNT/A-DP group during each re-treatment cycle at week 4 relative to re-treatment-baseline, based on both the investigators' and the subjects' in-clinic assessments.

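### The between-arm and McNemar tests that SAP 8.6.4 sets for response after re-treatment cannot inform; single-arm rates with confidence intervals should replace them

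*SAP*

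**What the plan says.** Endpoint numbers below follow SAP 4.3.

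- **Between-arm list (SAP 8.6.4).** The list opens with "Other additional secondary efficacy endpoints will be analyzed applying the appropriate statistical method for the comparison of both treatment arms". Two of its bullets are re-treatment proportions: "of subjects with an improvement of ≥ 2 points in FWS at maximum frown at 4 weeks after re-treatment" (endpoint 11; on a 0–3 scale a two-point fall always ends at 0 or 1) and "of subjects with ≥ 1 point reduction in FWS score at maximum frown at week 4 relative to re-treatment baseline" (endpoint 13). The tests named are CMH stratified by site and Pearson chi-square, or Fisher's exact test when data are sparse.
- **Treatment in the extension (SAP 3.3).** After cycle 1, "all subjects may enter the open label extension phase and will be dosed with BoNT/A-DP (20 U) for subsequent re-treatments".
- **Exclusion (SAP 8.6.4; also Protocol 12.4.2).** For the responder endpoint four weeks after re-treatment: "Subjects who were treated with placebo during the first treatment cycle are excluded from the analysis of this endpoint".
- **Second test for the same endpoint (SAP 8.1 and 8.6.4; Protocol 12.4.2).** A two-sided McNemar test at 0.05 compares week 4 after re-treatment with the preceding end of cycle visit, separately for each open-label cycle.
- **Scope sentence (SAP 8.6.4).** Every efficacy endpoint other than the re-treatment responder endpoint "will be analyzed for the first treatment cycle only". Yet SAP 4.3 defines endpoint 13, in the BoNT/A-DP group, "during each re-treatment cycle at week 4 relative to re-treatment-baseline".

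**The concern.** Efficacy after repeat treatment is part of the stated study purpose (Protocol 5.1) and an aim of the open-label part (Protocol 6.1, SAP 3.1). The analysis rules for it do not fit a design in which the control arm ends after cycle 1. A programmer following SAP 8.6.4 would meet a two-arm test with one arm, a paired test whose reference cell is always empty, and a sentence that removes endpoint 13 from the very cycles in which it is defined. Two competent programmers could produce different outputs.

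The exclusion has a reason in cycle 2, which is the first active injection for a placebo-first subject and so not a repeat treatment. It is not limited by cycle, however. In cycle 3 the same subject receives a second BoNT/A-DP injection, which is a genuine repeat treatment, and is still dropped.

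**Working it through.** The documents give no sample size or power for the re-treatment endpoints, so there is no planned figure for them to reproduce. The overall figures do reproduce: 300 / (1 − 0.15) = 352.9, or 353 enrolled (SAP 5).

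**1. Between-arm test**
- Endpoint 11: the BoNT-first group stays and the placebo-first group is excluded. The table has one group, so CMH, chi-square and Fisher are all undefined.
- Endpoint 13: if the BoNT/A-DP group in its definition means the randomised arm, there is again one group. If placebo-first subjects are included, both groups are on BoNT/A-DP 20 U.

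**2. McNemar test**
- SAP 3.3 accepts a visit as end of cycle only if investigator and subject both score FWS 2 or 3. Response requires 0 or 1. Responders at the reference visit are therefore zero by construction, apart from re-treatment given against the eligibility criteria, which SAP 6.6 treats as a protocol deviation.
- With b responders at week 4 and c = 0 at the reference visit, exact two-sided p = 2 × 0.5^b. For b = 5, p = 0.0625; for b = 6, p = 0.031.
- The asymptotic statistic is (b − c)² / (b + c) = b on 1 df. For b = 4, p = 0.046.
- Neither p-value depends on the number of subjects. With 225 subjects (the planned BoNT/A-DP figure in SAP 5) and a true response rate assumed to be only 5%, the chance of at least six responders is 97%.

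**3. Scope sentence against the rest of the SAP**
- Endpoint 13 is defined for every re-treatment cycle (SAP 4.3), and SAP 8.8.1 schedules a further analysis of it by remote or physical investigator assessment.
- Endpoint 9, FACE-Q satisfaction, is defined for each treatment cycle (SAP 4.3), and SAP 8.9 repeats it at the final analysis over all cycles.
- Only the re-treatment responder endpoint is excepted.

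**4. Size of the exclusion**
- Share: 75 / 300 = 25%, or 353 / 4 ≈ 88 of 353 randomised. BoNT-first: 353 × 3/4 ≈ 265.
- Entry to the extension, assumed equal to the BLESS I double-blind completion counts (Protocol 4.4.2.1): 500/531 = 94% and 160/177 = 90%. That gives about 249 BoNT-first and 80 placebo-first subjects.
- Placebo-first subjects reaching their second BoNT/A-DP injection in cycle 3, assuming 75–90% retention: 60 to 72.
- 95% half-width at an assumed 50% response, 1.96 × √(0.25/n): n = 249 gives 6.2 points; n = 249 + 60 = 309 gives 5.6; n = 249 + 72 = 321 gives 5.5.

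**The case against.** The strongest reply is that these are drafting slips in an exploratory section. Much of that stands. SAP 8.6.1.1 makes every additional secondary analysis exploratory, so no primary or key secondary conclusion changes. SAP 8.6.4 already provides for 95% intervals where appropriate and for analysis by cycle, and its plural wording on cycle-by-cycle analysis suggests that both re-treatment endpoints were meant. The exclusion was pre-specified in Protocol 12.4.2 and is sensible for cycle 2. None of this makes the listed test computable or the McNemar test informative.

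Three stronger readings are tempting, and the documents do not support them.

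- *Endpoint 11 has no comparator at all.* A within-subject comparator is specified. Its fault is that response is impossible at the reference visit.
- *A quarter of the extension data is lost.* The exclusion is written for one endpoint, and whether it reaches endpoint 13 is unclear. Open-label adverse events of placebo-first subjects are kept and attributed to BoNT/A-DP (SAP 8.7.2), safety analyses use the SAF (SAP 8.7), and no such exclusion is stated for antibody data or FACE-Q satisfaction.
- *A non-significant between-arm result, expected about 97.5% of the time, would pass for loss of effect.* That figure is simply 1 − 0.025 under equal response. It cannot apply to endpoint 11, and applies to endpoint 13 only if its definition is read as a contrast of randomised groups. A null difference between two groups on the same drug does not indicate loss of effect.

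**Conclusion.** The rules are wrong as written and should be corrected. The between-arm test is not computable for endpoint 11, and for endpoint 13 it is either one-group or drug against itself. The McNemar test is close to certain to succeed at any plausible response rate and carries no information. The scope sentence conflicts with endpoints 9 and 13. These conclusions follow from the text and need no assumptions beyond adherence to the end of cycle rule.

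The exclusion is a lesser matter. It covers about 25% of randomised subjects for endpoint 11 and is justified in cycle 2 but not from cycle 3. Recovering those subjects narrows the half-width by only 0.6 to 0.7 points, and that figure rests on assumed entry, retention and a 50% response. A pooled estimate is therefore optional. Removing the invalid tests, correcting the scope sentence and displaying placebo-first subjects from cycle 3 are not.

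**What to change.** In SAP 8.6.4:

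1. Remove the two re-treatment bullets from the CMH/chi-square list.
2. Drop the McNemar test (also in SAP 8.1), or label it non-informative.
3. Report endpoints 11 and 13 per cycle as single-arm rates with Wilson 95% intervals, the method SAP 8.6.2 already uses.
4. Show placebo-first subjects separately, by number of BoNT/A-DP injections received, counting them as repeat treatment from cycle 3. Keep any pooled estimate supplementary.
5. Add endpoint 13 and FACE-Q satisfaction to the exceptions in the scope sentence.

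Record the departures from Protocol 12.4.2 in SAP 9. The cost is SAP wording, one derived variable (active injection number) and slightly more tabulation; no new data are needed. SAP 8.9 does not list the re-treatment endpoints for the interim analysis, so their correction affects only the final one. The downside of pooling is that it mixes calendar time and adds placebo-first subjects who had to stay one cycle longer, which the separate display makes visible.
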